Prior to the start of the study, a randomization schedule will be constructed with block randomization using web-based software. Patients will then be allocated to one of two groups: Topical tranexamic acid or Placebo (saline). Group assignments will be concealed in opaque sealed envelopes with a numerical code of consecutive numbers reflecting patient enrollment. Envelopes will be stored with the pharmacy staff in charge of drug preparation. The pharmacy staff, which will have no patient contact, will remain un-blinded. The pharmacy staff will maintain the master key identifying which patients received the study drug and which patients received the placebo. Physicians, residents, hospital staff, and patients will be blinded to group assignment.

Eligible patients will be offered study enrollment following the screening protocol documented above in the “Screening procedures and who will perform them” section. The PI, Co-Investigator, [name], or the orthopedic surgery resident that is on call during the time of the patients’ hospital admission will obtain informed consent using the informed consent form approved by the IRB. Before a resident can serve as a consenter, he or she must first complete the training protocol found on the form “Educational Plan For Consenters.”

Topical (*Intra-Articular*) Tranexamic Acid and Transfusion Rates Following Hip Hemiarthroplasty

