If an LAR is required to provide informed consent, obtaining informed consent from the LAR and assent from the patient will occur in the patient's room with both the patient and LAR present so that communication regarding the study is not withheld from the patient despite his or her decisional impairment. If the LAR is not in the hospital, the LAR will be contacted in the manner that the orthopaedic surgery service contacted the LAR (e.g. by phone). If the LAR indicates that he or she is planning on coming to the hospital prior to the surgical intervention, informed consent for study inclusion will be sought at this time so that a face-to-face consent process can occur. If the LAR does not plan to come to the hospital before the surgical intervention or the LAR is unable to come to the hospital, the patient will not be eligible for study inclusion.

Once informed consent is obtained, the pharmacy will be contacted to allow provision of the study drug at the time of the procedure. When the patient is brought to the operating room, the pharmacy staff will open the numerical envelope assigned for the specific patient. The patient will undergo a hip hemiarthroplasty, according to the standard of care for a displaced femoral neck fracture. Surgical approach and implant selection will be left to the discretion of the attending surgeon. The only difference associated with study participation is that prior to wound closure, either a resident performing the surgery or the attending physician will introduce 1 gram

Topical (*Intra-Articular*) Tranexamic Acid and Transfusion Rates Following Hip Hemiarthroplasty

of tranexamic acid (APP Pharmaceuticals LLC, Schaumburg, IL) mixed with normal saline (0.9% NaCl) for a total volume of 50 cc or a 50 cc normal saline placebo into the wound. Of the 50 cc of the study drug or placebo, 25 cc will be introduced intra-articularly and 25 cc will be introduced under the fascial layer. When introducing either the study drug or placebo, the resident or attending physician should attempt to coat all surfaces with a thin layer of the aqueous solution. Wound closure technique will be left to the discretion of the attending surgeon. Post-operative venous thromboembolic prophylaxis will be left to the discretion of the attending surgeon.

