Warfarin requires reversal prior to surgery. Because there are multiple methods to achieve reversal from the elevated INR associated with warfarin use, which have different impacts on potential intra-operative and post-operative blood loss, inclusion of this population is not feasible. Dabigatran, rivaroxaban, and apixaban use constitutes exclusion because these drugs are relatively rare leading to potential imbalance of study groups and their effect on bleeding has not been adequately investigated in the literature. Because these drugs are relatively new, there is controversy associated with surgical timing when patients are taking these medications. Some providers elect to wait up to 48 hours since the last dose, while others operate immediately. There is no formal lab value that can monitor these drugs' impact on coagulation. As such, we have excluded these drugs.

Patients on anti-platelet medication (aspirin, clopidogrel, etc.) will be included in this study. Please refer to the protocol attachment “Anti-platelet Rationale” for a complete explanation. Use of these medications will be recorded as a covariate for analysis.

Topical (*Intra-Articular*) Tranexamic Acid and Transfusion Rates Following Hip Hemiarthroplasty

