Because patients sustaining femoral neck fractures rarely undergo surgical intervention in the same day, they are typically given a dose of either enoxaparin or heparin upon admission to prevent deep vein thrombosis given their injury and immobility. Patients receive this medication each day until the day of their surgical intervention, at which time this medication is held to prevent excessive intra-operative blood loss. The drug is resumed on post-operative day 1 for deep vein thrombosis prophylaxis. The drug insert for enoxaparin states, “significant anti-factor Xa activity persists for 12 hours following a 40 mg subcutaneous once a day dosing.” Because this medication is held on the day of surgery, there is greater than 12 hours from the last dose received until the surgical intervention. Patients who receive either enoxaparin or heparin will be included in the study. We will record the use of these medications (e.g. enoxaparin and heparin) and the interval between the last dose of medication and the surgical intervention for covariate analysis. Given how common the in-hospital use of these medications is in patients prior to undergoing hip hemiarthroplasty, we expect to achieve balanced groups through the process of randomization. Coagulation labs (PT/PTT/INR), when obtained prior to surgery, will be recorded to demonstrate similarity between the groups.

➤ *Describe length of subject’s participation in the study including number of visits, frequency of visits, and length of visits:*

Patients will be in the study for 4 to 6 weeks. This time period will encompass their inpatient hospital stay and their first two outpatient visits (one at approximately 2 weeks, a second at 4-6 weeks). These visits are the regularly scheduled post-operative visits that are part of routine care follow up. No extra time per visit or number of visits will be required as a result of study inclusion. The scheduled date of the patient’s post-operative outpatient visit occurring between 4 and 6 weeks will reflect the last day of study involvement.

➤ *Methods of Data Collection and Types of Data to be collected:*

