transfusion, will be analyzed using a two-group continuity corrected Chi-square test. Differences in packed red blood cell transfusion rates, amount of blood transfused, and inpatient cost will be analyzed using a two-group *t* test. Regression analysis will be used to model packed red blood cell transfusion outcomes against the main predictors (group allocation), adjusting for the effect of covariates (comorbidities, post-operative venous thromboembolism prophylaxis, etc.). Specifically, logistic regression will be used to model packed red blood cell transfusion as a binary outcome (yes or no) and multiple linear regression will be used to model packed red blood cell transfusion amounts and rates. The alpha level for all statistics will be set at 0.05.

5. Timetable

- Expected Start Date: 11/1/15
- General Time Table: 2 years
- Expected Completion Date: 10/31/17

6. Budget / resources:

We have received a Resident Research Project grant award from the Orthopaedic Research and Education Foundation (OREF). The pharmacy, which will play an essential role in this project, has been appropriately budgeted and is available to participate in this study.

7. Dissemination

We plan to disseminate the results of our research in the form of a peer reviewed journal article as well as application for presentation at a national society meetings.

8. References / Literature Review:

Topical (Intra-Articular) Tranexamic Acid and Transfusion Rates Following Hip Hemiarthroplasty

2. Eubanks JD. Antifibrinolytics in Major Orthopaedic Surgery (Review). *J Am Acad Orthop Surg.* 2010;18(3):132-8.

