APPENDIX A

Additional Details Pertaining to Study Design for Clinical Trials

Appendix A must be completed for investigator/student initiated research projects that require review by the convened board. For example, studies that use investigational test articles, that present more than minimal risk to subjects, or that involve prisoners, must be reviewed by the convened board.

Topical (*Intra-Articular*) Tranexamic Acid and Transfusion Rates Following Hip ~~Hip Arthroplasty~~

Note that for studies requiring review by the convened board the full board application must be completed, data safety monitoring must be addressed (e.g. by completion of Appendix B to the main application) and the Investigator Brochure and /or package insert must also be submitted if available.

1. *For a clinical trial (e.g. a Phase I, II or III study), the use of the intervention must be fully described e.g., the treatment regimen for use of drugs, placebo, medical device etc. Also include plans for receipt of test article, storage, dispensing and reconciliation.* : The intervention, the application of either 1 gram of tranexamic acid mixed with normal saline (0.9% NaCl) for a total volume of 50 cc or 50 cc of normal saline (0.9% NaCl) placebo, will occur intra-operatively just prior to wound closure. One half, or 25 cc, of either the study drug or the saline placebo will be applied intra-articularly. The second half, or 25 cc, will be applied under the fascia. When applying either the study drug or saline placebo, the resident performing the case or the attending surgeon will attempt to coat all exposed tissues with a thin layer of the aqueous solution. This is a one-time dose. Provision of the study drug (Tranexamic acid or saline placebo) will be provided by the hospital pharmacy. The pharmacy is responsible for the storing and dispensing the study drug.

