2. *Provide a description of known adverse events due to the intervention and the plan to deal with such adverse events (e.g. dose reduction, removal of device, removal from trial.)*: The package insert for Tranexamic acid provides a section on known adverse reactions with injection of the drug. Gastrointestinal disturbances (nausea, vomiting, diarrhea), allergic dermatitis, giddiness, and hypotension have been reported occasionally with intravenous injection. Worldwide post marketing reports include thromboembolic events (e.g. deep vein thrombosis, pulmonary embolism, cerebral thrombosis, acute renal cortical necrosis, and central retinal artery and vein obstruction) have been rarely reported. Convulsion, chromatopsia, and visual impairment have also been reported. However, due to the spontaneous nature of reporting of medical events and lack of controls the actual incidence and causal relationship of the drug and event cannot be determined.

There is no information regarding adverse reactions with topical use of tranexamic acid in the package insert. A review of the literature revealed a Cochrane review on topical application of tranexamic acid for the reduction of bleeding. Ker et al. reported topical use of the drug was not

Topical (*Intra-Articular*) Tranexamic Acid and Transfusion Rates Following Hip ~~Hemiarthroplasty~~

associated with an increased rate of complications. Topical use of the drug was associated with a relative risk of 0.28 (95% CI, 0.06-1.34; P = 0.11) for mortality, 0.33 (95% CI, 0.04-3.08; P = 0.33) for myocardial infarction, 0.33 (95% CI, 0.01-7.96; P = 0.49) for stroke, 0.69 (95% CI, 0.31-1.57; P = 0.38) for DVT, and 0.52 (95% CI, 0.09-3.15; P = 0.48) for pulmonary embolism [6]. These rates were comprised from 29 randomized control trials with 2,612 patients.

In the event an adverse event occurs, the surgeon and patient will be un-blinded and the patient will be treated according to standard medical practices. Adverse events will include mortality and thromboembolic events (pulmonary embolism, deep vein thrombosis, myocardial infarction, cerebrovascular accident, acute renal cortical necrosis, central retinal artery or vein obstruction).

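### The adjusted transfusion regressions include post-operative VTE prophylaxis, a post-randomisation variable; the main adjusted models should use only covariates fixed before the study drug is given.

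*Combined protocol and SAP*

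**What the plan says.** Section 4, Method(s) of data analysis, tests the primary outcome (transfused or not) with an unadjusted continuity-corrected chi-square test. It then adds a logistic regression for transfusion yes/no and multiple linear regressions for amounts and rates. Allocation is the main predictor in each, and the models are described as "adjusting for the effect of covariates (comorbidities, post-operative venous thromboembolism prophylaxis, etc".). The section does not rank the regressions against the chi-square test, and it sets 0.05 for every analysis.

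The timing comes from other places:

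- Appendix A, item 1: application of drug or placebo "will occur intra-operatively just prior to wound closure".
- Section 4, Study Procedures: "Post-operative venous thromboembolic prophylaxis will be left to the discretion of the attending surgeon".
- Section 4, Exclusion criteria (Therapeutics), on enoxaparin and heparin: "The drug is resumed on post-operative day 1 for deep vein thrombosis prophylaxis".

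Two statements bear on whether prophylaxis could depend on arm. Study Procedures says "Physicians, residents, hospital staff, and patients will be blinded to group assignment". Appendix A, item 2, says "In the event an adverse event occurs, the surgeon and patient will be un-blinded".

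The Therapeutics text also names pre-operative covariates. On antiplatelet drugs: "Use of these medications will be recorded as a covariate for analysis". On enoxaparin and heparin, it records use and "the interval between the last dose of medication and the surgical intervention for covariate analysis".

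**The concern.** Adjusting a randomised comparison is safe when the covariates cannot have been influenced by treatment. Prophylaxis given after surgery lacks that guarantee. The study drug is meant to reduce bleeding, and bleeding or a low postoperative hemoglobin is a plausible reason to delay or change an anticoagulant. If that happens, prophylaxis carries information about the drug's own effect, and holding it constant removes part of that effect. Randomisation does not protect an estimate conditioned on such a variable.

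At stake is how the adjusted estimates are read. An effective drug could look weaker in the adjusted analysis than in the primary one, and a reader could not tell whether chance imbalance or the adjustment itself explained the difference.

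**Working it through.** **1. The plan's own figure.** Inputs from Section 4, Sample size and justification: 35% versus 10%, two-sided 0.05, 80% power, continuity-corrected chi-square.

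- Uncorrected n' = [1.960·√(2·0.225·0.775) + 0.842·√(0.35·0.65 + 0.10·0.90)]² / 0.25² = 42.6.
- Corrected n = (n'/4)·[1 + √(1 + 4/(n'·0.25))]² = 50.3, rounded up to 51 per arm, as stated.
- Odds ratio = (0.35/0.65)/(0.10/0.90) = 4.846, as stated. Drug versus placebo it is 1/4.846 = 0.206.

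The primary test contains no covariates, so nothing below changes the 51.

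**2. Yardstick.** Expected counts per arm are 17.85 transfused and 33.15 not (placebo), and 5.1 and 45.9 (drug). The SE of the log OR is √(1/17.85 + 1/33.15 + 1/5.1 + 1/45.9) = 0.551. The unadjusted 95% CI for 0.206 is 0.07 to 0.61.

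**3. Order of events.** Randomisation comes first, then the drug before closure, then prophylaxis from post-operative day 1. The covariate is therefore realised after both randomisation and drug. The documents do not say when the surgeon decides on it.

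**4. A case that can be checked by hand: prophylaxis responds to transfusion only.** Assume 90% use in patients not transfused and 60% in those transfused, in both arms.

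| Stratum | Placebo: transfused / not | Drug: transfused / not | OR | Risk difference |
|---|---|---|---|---|
| Prophylaxis | 0.210 / 0.585 | 0.060 / 0.810 | 0.206 | 0.069 − 0.264 = −0.195 |
| No prophylaxis | 0.140 / 0.065 | 0.040 / 0.090 | 0.206 | 0.308 − 0.683 = −0.375 |

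The adjusted OR is unchanged. Least squares weights each stratum by its size times p(1−p), where p is the share on drug: 0.415 and 0.080. The pooled difference is (−0.195·0.415 − 0.375·0.080)/0.495 = −0.224, against −0.250 unadjusted, a shrinkage of 10%. With 80% and 30% use the same steps give −0.203, a shrinkage of 19%. The logistic model still loses precision: in simulated trials of 51 per arm, its power fell from 89.4 to 85.5% (90 to 60%) and from 88.3 to 79.7% (80 to 30%).

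**5. Prophylaxis responds to bleeding.** Two separate illustrations were run, both calibrated to 35% and 10%. Every link is assumed.

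*Step response* (use drops when bleeding is heavier; bleeding–transfusion correlation 0.5 to 0.9). Shift = ln(adjusted OR/0.206)/0.551.

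| Assumed use, lighter to heavier bleeding | Adjusted OR | Shift toward the null, in SE |
|---|---|---|
| Unrelated to bleeding | 0.207 | about 0 |
| 99 to 95%, 98 to 90% | 0.205–0.211 | −0.01 to 0.04 |
| 90 to 60% | 0.215–0.223 | 0.08 to 0.14 |
| 80 to 30% | 0.226–0.244 | 0.17 to 0.31 |
| 95 to 20% | 0.289–0.315 | 0.61 to 0.77 |

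At correlation 0.7, the power of the logistic test changed from 88.9 to 88.1% (98 to 90% use), 88.5 to 84.3% (90 to 60%) and 88.1 to 78.2% (80 to 30%).

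*Graded response* (log-odds of prophylaxis fall by g per SD of bleeding; prophylaxis has no effect of its own). Placebo versus drug, the adjusted OR is 4.85 at g = 0, 4.76 at 0.25, 4.55 at 0.5, 3.99 at 1 and 3.11 at 2. The unadjusted value is 4.846 throughout.

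**6. No drug effect.** In these set-ups the adjusted OR stayed at about 1, and adjusted tests rejected in 4.6 to 6.3% of simulated trials against 4.3 to 6.1% unadjusted. The un-blinding route was not simulated.

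**7. Room in the model.** Expected transfused patients: 51·0.35 + 51·0.10 = 22.95, about 23. As a rule of thumb (an assumption here), that supports about 2 terms at 10 events per term, or 4 to 5 at 5 per term, allocation included.

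**The case against.** **The bias may well be nil.** Surgeons are blinded, and the Therapeutics text describes resuming a drug most patients already had before surgery. That fits a routine barely related to bleeding, for which the near-uniform row is the closest match. This stands, and no size can be claimed. It does not turn prophylaxis into a baseline covariate: blinding hides the arm, not visible bleeding.

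**The choice may precede the drug.** This also stands as far as it goes. Discretion is stated without a time, and day 1 dates administration, not decision. A reader might infer that the surgeon chooses after the drug; the documents do not say so. They also do not fix the choice beforehand.

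**Prophylaxis may be a bleeding-risk factor in its own right.** If its use is unrelated to arm and bleeding, adjusting helps slightly. With 50% exposure assumed, simulated power rose from 88.7 to 88.9% (prophylaxis OR 2) and from 87.6 to 89.9% (OR 4). This is a fair reason to keep it in a sensitivity analysis.

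**Un-blinding.** A reader might sum the rates in the stopping-rule table (PE 1%, DVT 3%, MI 1.9–3.1%, stroke 0.1–1.5%) to 6.0–8.6%, or 3 to 4 of 51 patients per arm, and treat all of them as a route from arm to prophylaxis. That overstates it. Those rates cover 4 to 6 weeks and draw partly on 30-day and 90-day sources. Only events early enough to alter prophylaxis and be linked with transfusion matter, and the documents give no count of these.

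**The open list.** A reader might also infer that the list ending in etc. contradicts the Therapeutics text, or leaves the covariates unknown. Read together, the two sections name most of them. What is missing is detail, and there is no conflict.

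**Conclusion.** The point holds in a limited form. A variable realised after the study drug is named as an adjustment for the treatment effect. This can pull the adjusted estimate toward no effect or cost precision if prophylaxis responds to bleeding, postoperative hemoglobin or transfusion. If it responds to none of these, there is no bias.

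The size is unknown and may be nil. Near-uniform use gives at most about 0.04 SE and about 1 point of power. The larger shifts show direction only, since no section supports links of that strength. The two stronger conclusions, that the adjusted result will be materially biased or that the trial's main conclusion is at risk, are not supported. The primary chi-square test and the 51 per arm do not depend on these models. A false-positive risk was not seen in the cases simulated, which do not include un-blinding.

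The change is still worth making, because it removes a possible bias at almost no cost.

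**What to change.** In Method(s) of data analysis:

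1. Remove post-operative VTE prophylaxis from the main logistic and linear models.
2. Restrict their covariates to variables fixed before the study drug is given. Candidates the plan already names are antiplatelet use, pre-operative enoxaparin or heparin use with the interval since the last dose, and pre-existing comorbidities. The interval exists only in patients given the drug, so it needs a use indicator beside it.
3. Keep the list short, given about 23 expected transfused patients. The exact choice is the sponsor's.
4. Report prescribed chemoprophylaxis by arm, or add it only in a sensitivity analysis labelled as conditioning on a post-treatment variable.
5. State that the regressions support the unadjusted primary test, since the section does not now say so.

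The cost is a few sentences and a cross-reference to the Therapeutics text. The variables are already collected, and the primary test, sample size and patient care do not change. The downside is a little lost precision in the main adjusted model if prophylaxis is an independent bleeding-risk factor unrelated to arm: 0.2 to 2.3 points of power in the illustration above. The sensitivity analysis covers that case.

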Following surgery, the patient will be admitted to the hospital per the standard of care. The length of inpatient stay following this procedure is approximately 3 to 4 days, however this may vary. Following discharge from the hospital, patients will follow up with the treating surgeon at two outpatient visits (one at approximately 2 weeks, a second at 4-6 weeks). These visits are the regularly scheduled post-operative visits as part of routine care. The methods and types of data to be collected are described in the “Methods of Data Collection” section of this protocol.

➤ *Sample size and justification:*

A sample size calculation was conducted to determine the number of patients needed to observe a difference in packed red blood cell transfusion rates. In the last two fiscal years at UCHC a hip hemiarthroplasty has been performed in 84 patients, 29 of which required packed red blood cell transfusions (34.5%). We queried the Health Care Utilization Project Database, a stratified 20% national sample of over 7,000,000 hospital stays at over 1,000 hospitals in 46 states, to estimate national rates of packed red blood cell transfusion. In this sample, 14,813 of 45,800 (32.3%) patients undergoing hip hemiarthroplasty in 2011 required a packed red blood cell transfusion. Given these numbers, we used a value for packed red blood cell transfusion rate of 35% for patients that receive placebo. The literature has shown packed red blood cell transfusion rates with use of the drug in an orthopedic setting in similar populations to range from 12.5% to 1%. Accordingly, we selected a packed red blood cell transfusion rate of 10% in patients receiving tranexamic acid. A two group continuity corrected Chi square test with a 0.05 two-sided significance level will have 80% power to detect the difference between packed red blood cell

Topical (*Intra-Articular*) Tranexamic Acid and Transfusion Rates Following Hip ~~Hemiarthroplasty~~

transfusion rates of 35% and 10% (odds ratio of 4.846) when the sample size in each group is 51 (102 total).

➤ *Explain on what basis it is reasonable to assume that the sample size will be obtained:*

The number of hip hemiarthroplasties performed annually has been increasing. In the last fiscal year, 49 hip hemiarthroplasties were performed at UCHC. With a 2-year study period and the possibility that the study may be extended to neighboring facilities (St. Francis Medical Center), it is reasonable to assume the sample size will be obtained.

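### The supportive adjusted logistic model has about 23 expected events, an open covariate list and no stated estimator; a Firth fit with a short fixed list would be a cheap, minor improvement

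*Combined protocol and SAP*

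**What the plan says.** The combined protocol and SAP, under Method(s) of data analysis, makes an unadjusted continuity-corrected chi-square test the primary comparison of transfusion rates. It then adds a regression on group allocation with covariate adjustment: "logistic regression will be used to model packed red blood cell transfusion as a binary outcome (yes or no". The covariates named there are comorbidities (no number given) and postoperative thromboembolism prophylaxis, and the list ends in an open "etc."

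The text under Exclusion criteria adds to it. On anti-platelet drugs: "Use of these medications will be recorded as a covariate for analysis". On enoxaparin and heparin, the plan will record use of the drugs and "the interval between the last dose of medication and the surgical intervention for covariate analysis". That makes five kinds of covariate in all.

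Sample size and justification gives the design: "A two group continuity corrected Chi square test with a 0.05 two-sided significance level will have 80% power to detect the difference" between "transfusion rates of 35% and 10% (odds ratio of 4.846) when the sample size in each group is 51". The significance rule is general: "The alpha level for all statistics will be set at 0.05". No estimator, penalty, limit on the number of terms or rule for separation is stated.

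**The concern.** Fitted by maximum likelihood (ML) with few events per parameter, logistic regression tends to give odds ratios too far from 1. Here the events are few and the covariate list has no upper bound. If the drug works, the adjusted odds ratio would tend to look somewhat more favorable than the truth. A reader who compares it with the unadjusted result might credit the difference to adjustment. At stake is the size of a supporting estimate for the primary outcome, not the primary test.

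**Working it through.** **Inputs from the plan.** The placebo rate is 35% ("we used a value for packed red blood cell transfusion rate of 35% for patients that receive placebo") and the drug rate 10% ("we selected a packed red blood cell transfusion rate of 10% in patients receiving tranexamic acid"), with 51 per group and two-sided alpha 0.05.

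**The plan's own figure.** With a mean rate of 0.225, the uncorrected size per group is

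[1.96 x sqrt(2 x 0.225 x 0.775) + 0.842 x sqrt(0.35 x 0.65 + 0.10 x 0.90)]² / 0.25² = 42.6.

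The continuity correction gives (42.6/4) x [1 + sqrt(1 + 4/(42.6 x 0.25))]² = 50.3, so 51. This matches the plan. Power at 51 is 80.7% by the corrected approximation and 81.6% by exact enumeration. The odds ratio is (0.35/0.65)/(0.10/0.90) = 4.846, and its log is 1.578.

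**Events.** 51 x 0.35 + 51 x 0.10 = 17.85 + 5.10 = 22.95.

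**Events per parameter.** Five covariates plus group: 22.95/6 = 3.8. Six plus group, if two comorbidities or the two heparin-type drugs are separate terms: 22.95/7 = 3.3.

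**Simulation.** 10,000 trials per row, calibrated to marginal rates of 35% and 10%. Assumptions not in the documents: independent covariates, one continuous and the rest binary with prevalence 10-50%, each with log odds ratio 0 or 0.5. The ML columns leave out the roughly 0.3% of trials with separation. Bias is measured against the true conditional log odds ratio.

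| Covariates (log OR each) | True | ML mean (bias) | ML median (bias) | Firth mean (bias) | RMSE, ML to Firth |
|---|---|---|---|---|---|
| 5 (0) | -1.578 | -1.759 (11.4%) | -1.712 (8.5%) | -1.579 (0.1%) | 0.676 to 0.575 |
| 5 (0.5) | -1.695 | -1.916 (13.0%) | -1.856 (9.5%) | -1.700 (0.3%) | 0.742 to 0.608 |
| 6 (0) | -1.578 | -1.783 (13.0%) | -1.733 (9.8%) | -1.579 (0.0%) | 0.698 to 0.578 |
| 6 (0.5) | -1.704 | -1.960 (15.0%) | -1.891 (11.0%) | -1.708 (0.2%) | 0.780 to 0.617 |

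The Monte Carlo standard error of the ML mean is 0.007, about 0.4% of the true value. With six covariates, half binary at 30% prevalence and half continuous, each with log odds effect 0.3, two smaller simulations gave mean biases of 15.8% (2,500 trials) and 14.5% (3,000 trials); the latter had a median bias of 11.7%. Hence the ranges 11-16% in mean and 8-12% in median.

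**RMSE gain.** From (0.676 - 0.575)/0.676 = 15% to (0.780 - 0.617)/0.780 = 21%.

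**No drug effect, six covariates.** Mean bias is zero. Rejection rates are 5.6-5.8% (Wald) and 6.0-6.4% (likelihood ratio) for ML, against 4.1% (Wald) and 5.0-5.2% (penalized likelihood ratio) for Firth.

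**Power, six covariates.** Wald falls from 86.6-88.8% to 83.6-85.7%; likelihood ratio falls from 88.3-90.0% to 85.8-88.0%.

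**ML interval coverage.** 95.7-96.3% in the four rows of the table, and 94.2-94.4% with no drug effect.

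**Non-collapsibility.** In the last row the true conditional value is -1.704 and the marginal value -1.578. Of the distance from the marginal value to the ML mean, 1.960 - 1.578 = 0.382, a part of 1.704 - 1.578 = 0.126 is non-collapsibility and 0.256 is bias.

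**The case against.** The model is supportive. The trial is sized on the chi-square test and judged by it, and neither changes. With six covariates the bias is 0.20 to 0.26 on the log scale against a standard deviation of 0.67 to 0.74, about a third, and intervals keep their coverage. All of this stands, and it is why the point is minor.

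A short covariate list alone would also do part of the work. That is true, but only part: with a single covariate the mean bias is still about 6%.

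Several stronger readings are tempting, and the documents do not support them:

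- **That the plan commits to ML with at least six covariates.** It names five kinds and an open remainder; comorbidities could be one index. The Exclusion criteria text does not mention the logistic model. ML is the usual meaning of an unqualified logistic regression, not a stated choice.
- **That the overstatement is 24% or 30%.** Those sizes arise in simulations with ten or twelve covariates, a number with no anchor in the plan.
- **That any gap between adjusted and unadjusted odds ratios is bias.** Part of it is non-collapsibility, which no estimator should remove.
- **That a penalized fit is free, or that any penalty will serve.** Firth costs some power. A ridge penalty (lambda = 1) that included treatment understated the log odds ratio by about 22%.

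**Conclusion.** The concern holds as a minor point and a cheap improvement. Under ML with five or six covariates, the planned rates imply a treatment log odds ratio overstated by about 11-16% in mean and 8-12% in median. With six covariates the median estimated odds ratio would be about 0.18 against a true 0.21, or 0.15 against 0.18, depending on how prognostic the covariates are.

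This rests on three assumptions: the ML reading, the number of terms, and the simulated covariate distributions and effects. It also rests on the planned effect. At 35% against 20% with six covariates the bias was 0.09 on the log scale, and with no effect it vanishes. The primary analysis and the sample size are sound on this point.

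**What to change.** Under Method(s) of data analysis, state that the adjusted logistic model uses a short, closed, pre-specified covariate list and is fitted by Firth penalized likelihood, with penalized profile-likelihood tests and confidence intervals. Wald tests should not be used after the Firth fit, since they are conservative (4.1%), and treatment should not carry a ridge penalty. If a standardized risk difference is reported as well, use an intercept-corrected Firth fit: plain Firth fitted probabilities ran about 1.5 percentage points above the observed rate.

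The change takes one or two sentences and needs no extra patients or data. The price is about 2-3 points of nominal power in this supportive analysis, partly from removing ML's slightly inflated type I error. In return, mean bias is close to zero, RMSE is about 15-20% lower, and estimates stay finite if separation occurs.
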